14. REGULATORY, ETHICAL, AND STUDY OVERSIGHT CONSIDERATIONS

14.1 Regulatory and ethical aspects

The study protocol is designed and will be conducted to ensure adherence to the principles and procedures of Good Clinical Practice and to comply with Italian laws, as described in the following documents and accepted, with their signature, by the study investigators: 1. ICH harmonized tripartite guidelines for good clinical practice 1996.2. Directive 91/507 / EEC, The Rules Governing Medicinal Products in the European Community. 3. Legislative Decree No. 211 of 24 June 2003.4. Legislative Decree n.200 November 6, 2007.5. D.M. 21 December 2007.6. AIFA Determination March 20, 2008. All essential clinical documents will be kept to demonstrate the validity of the study and the integrity of the data collected.

All the document e protocol, protocol amendments, ICF, and other relevant documents must be submitted to an IRB/IEC by the investigator and reviewed and approved by the IRB/IEC before the study is initiated.

14.2 Financial disclosure

Finance and insurance are addressed in the Investigator and/or CRO agreements, as applicable.

14.3 Informed consent process

Participant's informed consent/assent (ICF) must be obtained and documented in accordance with local regulations, ICH-GCP requirements, and the ethical principles that have their origin in the principles of the Declaration of Helsinki. Prior to obtaining informed consent, information should be given in a language and at a level of complexity understandable to the participant in both oral and written form by the Investigator (or designee). Each participant will have the opportunity to discuss the study and its alternatives with the Investigator. Prior to participation in the study, the ICF should be signed and personally dated by the participant, or his/her legal representative.

The participant or his/her legal representative must receive a copy of the signed and dated Informed Consent form. As part of the consent process, each participant must consent to direct access to his/her medical records for study-related monitoring, auditing, IRB/IEC review, and regulatory inspection. If the ICF is amended during the study, the Investigator must follow all applicable

regulatory requirements pertaining to the approval of the amended Informed Consent form by the IRB/IEC and use of the amended form.

The participant may withdraw his/her consent to participate in the study at any time. Consent may be waived with documented approval as per local guidelines, for example in the case where only routinely collected data from medical records are collected for this study.

14.4 Data protection

The participant must be informed that his/her personal study-related data will be used by the local Principal Investigator in accordance with local data protection law. The level of disclosure must also be explained to the participant who will be required to give consent for their data to be used as described in the informed consent.

Participants will be assigned a unique identifier by the Promotor. Any participant records or datasets that are transferred to the sponsor will contain the identifier only; participant names or any information which would make the participant identifiable will not be transferred.

The electronic case report form (eCRF) will be provided using RedCap® software of the University of Bologna/CINECA. Investigators from participating study sites log into the system with username and a safe password including letters, numbers, and symbols.

Investigators will be informed about handling of their personal data and their IP and location during the registration process

The data collection should be performed also retrospectively after a patient case has been completed (treatment or follow-up is finished or patient's death). This process will be compliant with all applicable European and German federal data protection regulations, including EU directive 2016/679 and the German DS-GVO.

14.5 Description of the data collected

Only data that is strictly necessary and relevant to meet the objectives of the research are collected.

The data collected via the medical file as part of the research falls into the categories following:

Demographics data: age, sex, race, education, cigarette smoking, usual residence.

Detailed clinical data, including about possible previous and concomitant illnesses, medical findings and therapies in the context of SARS-CoV-2 infection.

Data collected by self-administered questionnaires: questionnaires to address the functional status, respiratory impairment, mental health, and socio-economic issues with related behavior.

Data will be collected by a standardized electronic case report form (eCRF) and managed using REDCap capture tool. Collected data will be periodically checked for accuracy by an investigator of the coordinating unit (UNIBO). Queries for incongruous or missing data will be submitted to

investigators. There will be 12 mailing cycles a year in which baseline and post-COVID-19 follow-up and/or post vaccination monitoring information will be requested. This policy will ensure that the cohort statistics will be based on a data set that is current, complete and as accurate as possible.

14.6 Data quality assurance

All participant data relating to the study will be recorded on the electronic-CRF. The Investigator is responsible for verifying that data entries are accurate and correct by physically or electronically signing the eCRF or paper CRF. The local investigator must maintain accurate documentation (source data) that supports the information entered in the eCRF or paper CRF. The local investigator must permit study-related monitoring, audits, IRB/IEC review, and regulatory agency inspections and provide direct access to source data documents. The promotor is responsible for the data management of this study including quality checking of the data as described above in study procedures' section.

14.7 Source Document

All source documents must be accurate, clear, unambiguous, permanent, and capable of being audited. They should be made using some permanent form of recording (typing, printing, optical disc). They should not be obscured by correction fluid or have temporary attachments (such as removable self-stick notes). Source documents are original records in which raw data are first recorded. These may include hospital/clinic/general practitioner records, charts, diaries, x-rays, laboratory results, pharmacy records, care records, ECG or other printouts, questionnaires, or video, for example. Source documents should be kept in a secure, limited access area.

14.8 Study and site closure

The study will start after the approval by the ethics committee approximately on April 2021 and it will end 12 months after the last patient enrollment. The overall duration of the study is 26 months.

14.9 Publication policy

The PI is responsible for the final publication of data. Authors must satisfy all of the following ICMJE authorship criteria: 1. Substantial contributions to conception or design of the work; or the acquisition, analysis, or interpretation of data for the work; AND 2. Drafting the work or revising it critically for important intellectual content; AND 3. Final approval of the version to be published; AND 4. Agreement to be accountable for all aspects of the work in ensuring that questions related to the accuracy or integrity of any part of the work are appropriately investigated and resolved. Data collection, general supervision of the research group, or overseeing the conduct of the study alone

does not justify authorship. Publications will be planned by the PI and the scientific and statistical committees. Publication of partial or local data must be approved by the PI.

14.10 Amendments or any other modification

Modifications to the protocol will be made as amendment. No other modality is allowed. Any modification will be recorded in the "Clinical Study Report" Archiving documents. The principal investigator is responsible for archiving and storing the essential documents during all the period of study according by current legislation and GCP.

15. ADD-ON SUBSTUDIES

15.1 Pregnant Women (PW) Cohort for evaluation of risks of congenital malformations and other adverse pregnancy outcomes after Zika virus infection (part of ZIKAlliance) - SARS-CoV-2 sub study.

15.2 Children (CH) cohort for the evaluation of developmental and neurological abnormalities in infants born to mothers residing in areas with Zika virus transmission during pregnancy (part of ZIKALLIANCE) - SARS-CoV-2 sub study.

15.3 Epidemiologic study of respiratory infections by novel coronavirus (SARS-CoV-2) in the paediatric population

ANNEX 1a and ANNEX 1b – Time points for the socio-economic questionnaires

Day 0 of this questionnaire refers to the first contact with the patient. Day 0 may be allocated in different time points depending on the cohort and study. **For WP2** patients, Day 0 is the first prospective follow-up point, which could be month 3, month 6, month 12 or month 18, depending on the time of infection diagnosis. **For WP4**, Day 0 corresponds to either the first contact for an underlying condition visit or to vaccine administration. If Day 0 cannot correspond to the time of vaccine administration then Day 0 will correspond to the first post-vaccination follow-up. Information will be collected at least at two time points for each patient, unless Day 0 corresponds to month 18 in WP2 (in this case it is unfeasible to interview the patient again). The two time points will be ≈ 12 months apart unless not feasible, that is when Day 0 is at month 12 or 18 for WP2.

[figure not shown]
The second time point will be:

- **For WP2**, month 18. For example, if the first prospective data collection point corresponded to the follow-up visit at month 12, then the second and last contact with such patient would take place at month 18.
- **For WP4**, month 12, which corresponds to either the 12 month vaccination follow-up or the visit of end of study.

[figure not shown]
In addition to the two time points, information could also be collected ≈ 6 months after Day 0 whenever possible (although not mandatory).

WP2

In the context of the scheduled SARS-CoV-2 infection follow-up assessments.

WP4

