| Metagenomic sequencing | X | | X | | |
| Questionnaires¹ | | | | | |
| Risk perception and behavior | X ¹ | | | X | X |
| Socio-economic indicators | X ¹ | | | X | X |
| Use of resources (COVID-19 unrelated) | X ¹ | | | X | X |
| Adverse Events dedicated questionnaire | | X | X | X | X |
| Immune response | | | | | |
| Quantitative Ab anti-S IgG ⁵ | X | X | X | X | X |
| Qualitative Ab anti-N IgM+IgG ⁵ | X | | | | |
| Anti-SARS-CoV-2 sero-neutralization | X | X | X | X | X |
| Cytokine / chemokines | X | X | X | X | X |
| Anti-SARS-CoV-2 cell immunity | | X | | X ⁶ | X ⁶ |

Footnotes

Modular data capture according to level of commitment (level I, level II).

| | |
|----------|---|
| Level I | Assessments in level I are core and should be prioritized |
| Level II | Customized according to the feasibility of each cohort |

*3, 6 and 12 months counted from the 1st dose.

¹For centers able to follow patients since the administration of the first and second vaccination doses the baseline information and the risk perception behavior should be collected at one of these time-points, in the other cases such information should be collected during the first post-vaccination follow-up.

²The assessment at 2nd dose is mandatory in patients who will receive such dose within 8-12 weeks after first dose (current AstraZeneca vaccination schedule).

³If COVID-19 diagnosis, assessments reported in Table 1 are required.

⁴Relevant new medical events or worsening of previous conditions, including new malignancies (type of cancer, overall stage, Kaposi skin-visceral, Lymphoma localization-type, Leukemia lymphoid-myeloid acute-chronic), deep venous thrombosis, pulmonary embolism, infections (including a new SARS-CoV-2-infection during follow-up)

⁵At least one time-point at 1st and 2nd dose is required.

⁶At least one of the three timepoints (month 3, month 6, month 12) is required.

⁷At least one of the four timepoints (2nd dose, month 3, month 6, month 12) is required.

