11. STUDY PROCEDURES

In Figure 1, a study work flow is shown.

Figure 1: study work flow

All included patients will be evaluated during the scheduled visits for the underlying condition. During such visits, the following actions are required:

- Distribution of a questionnaire to capture the impact of COVID-19 pandemic on the socio-economic indicators, on the access to health care services, and to investigate risk perception and behavior towards preventing infection and COVID-19 disease, including vaccine acceptance. This questionnaire should be administered at two different time-points with an interval of at least 6 months to capture changes in behavior over the study period (Annex 1a or Annex 1b in case of children cohorts).

- Distribution of psychological scale questionnaires to investigate the impact of lockdown measures on mental health (Annex 2).
- Screening for past and/or current COVID-19 disease by medical interview, serology determination and nasopharyngeal swab or saliva specimens' collection.
- Collection, processing and storage of plasma for cytokine and chemokine analysis.
- Collection, processing and storage of serum for the subsequent sero-neutralization and type I IFNs autoantibodies detection.
- Collection, processing and storage of PBMCs for the subsequent anti-COVID-19 cellular immunity analysis.
- Collection, processing and storage of whole blood for genetic and epigenetic analysis.
- Collection, processing and storage of nasopharyngeal samples for SARS-CoV-2 detection and variant identification if clinically relevant.
- Collection, processing and storage of stool samples for metagenomic sequencing.
- In immunocompromised fragile cohorts, laboratory tests to assess the baseline “net state of immunosuppression” including whole blood count, lymphocyte differentiation, immunoglobulin levels, and complement (C3) levels should be done at the baseline (first clinical evaluation).

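### Annex 1 promises socio-economic interviews about 12 months apart, but its own timing rules also give nominal gaps of 15 months (WP2) and 9 months (vaccinated WP4) that it does not list as exceptions

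*Protocol*

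**What the plan says.** The protocol's Annex 1a/1b section on time points gives a target interval with a short list of exceptions: "The two time points will be ≈ 12 months apart unless not feasible, that is when Day 0 is at month 12 or 18", the last words applying to WP2.

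The same section lets the first interview float:
- In WP2, Day 0 is the first prospective follow-up, "which could be month 3, month 6, month 12 or month 18, depending on the time of infection diagnosis".
- In WP4, Day 0 is a first visit for the underlying condition or the vaccination itself. Failing that, "If Day 0 cannot correspond to the time of vaccine administration then Day 0 will correspond to the first post-vaccination follow-up".

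The second interview is fixed:
- In WP2 it is month 18. For a patient who starts at month 12, "then the second and last contact with such patient would take place at month 18". A second interview is waived only for the latest start: "unless Day 0 corresponds to month 18 in WP2 (in this case it is unfeasible to interview the patient again".
- In WP4 it is "month 12, which corresponds to either the 12 month vaccination follow-up or the visit of end of study".

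Three other places bear on this. Section 11 asks for a looser interval, with the questionnaire "administered at two different time-points with an interval of at least 6 months". The footnotes to Table 2 in Section 3.2 count the post-vaccination months from the first dose. For centres that cannot follow patients from the doses, footnote 1 adds that "in the other cases such information should be collected during the first post-vaccination follow-up". Annex 1a requires the interview date to be recorded each time.

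**The concern.** The first interview can move and the second cannot, so the interval cannot be the same for everyone. The stated 12 months holds only for some starting points, and the listed exceptions do not cover the rest.

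Risk perception over time and socio-economic impact are study objectives (Section 7). Section 13 proposes methods such as difference-in-differences that draw on variation over time. In vaccinated WP4 patients, the length of the gap follows from whether the centre sees patients at the doses. If perceived risk, behaviour or income drifts over calendar time in everyone, unadjusted change would then differ between the two kinds of centre for no reason other than interval length.

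There is a second, more practical cost. The follow-up form in Annex 1a asks about care disruption, financial difficulty and aid received over the previous 6 or 12 months. Neither period fits a gap of 9 or 15 months.

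**Working it through.** **Inputs.** WP2 Day 0 at month 3, 6, 12 or 18, second interview at month 18 (Annex 1). WP4 Day 0 at dose 1 or at the first post-vaccination follow-up, second interview at month 12 (Annex 1). Post-vaccination visits at 3±1, 6±2 and 12±3 months from dose 1 (Section 11, Table 2). COVID-19 follow-up visits at 3±1, 6±1, 12±2 and 18±3 months (Table 1). WP2's own schedule is not shown, so Table 1 stands in for its windows.

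**Formula.** Nominal gap = month of second interview − month of Day 0. Shortest gap = earliest second − latest Day 0. Longest gap = latest second − earliest Day 0.

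**The plan's own figure.** Twelve months is reproduced for two starts: WP4 at dose 1 (12 − 0 = 12) and WP2 at month 6 (18 − 6 = 12).

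| Day 0 | Second interview | Nominal gap | Window extremes | Listed exception? |
|---|---|---|---|---|
| WP2 month 3 (2–4) | 18 (15–21) | 15 | 15−4 = 11 to 21−2 = 19 | No |
| WP2 month 6 (5–7) | 18 (15–21) | 12 | 15−7 = 8 to 21−5 = 16 | Not needed |
| WP2 month 12 (10–14) | 18 (15–21) | 6 | 15−14 = 1 to 21−10 = 11 | Yes |
| WP2 month 18 | none | – | – | Yes |
| WP4 dose 1 | 12 (9–15) | 12 | 9 to 15 | Not needed |
| WP4 month 3 (2–4) | 12 (9–15) | 9 | 9−4 = 5 to 15−2 = 13 | No |
| WP4 month 6 (4–8), assumed first visit | 12 (9–15) | 6 | 9−8 = 1 to 15−4 = 11 | No |

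The annex does not name month 6 as a WP4 start. That row assumes a patient whose first post-vaccination visit is the 6-month one. For WP4 patients whose Day 0 is an underlying-condition visit and whose second point is the end-of-study visit, no fixed gap can be derived.

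**Effect on unadjusted change.** Suppose an indicator drifts linearly by d per 12 months in every patient. Change over g months is d × g/12, so the spurious difference from a 12-month patient is d × (1 − g/12):
- g = 9: 1 − 9/12 = 0.25, giving 0.25d
- g = 6: 1 − 6/12 = 0.50, giving 0.50d

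The documents give no value for d.

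**Recall period.** With a 9-month gap, 12-month recall reaches 12 − 9 = 3 months back before Day 0, and 6-month recall leaves 9 − 6 = 3 months uncovered. With a 15-month gap, 12-month recall leaves 15 − 12 = 3 months uncovered and 6-month recall leaves 15 − 6 = 9.

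**Schedule tables.** In Table 2 the questionnaire rows are marked at dose 1, month 6 and month 12 and are blank at month 3, although footnote 1 and Annex 1 can place the first interview there. In Table 1 the vaccine-acceptance, socio-economic and resource-use rows are marked at months 3, 12 and 18.

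**The case against.** Several points on the other side are sound.

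- **Twelve months can be reached within the windows.** A WP4 patient starting at month 3 can be interviewed at month 15, inside 12±3. A WP2 patient starting at month 3 can also be interviewed at month 15, inside 18±3. This stands, and it makes the repair easy. But the annex names nominal months 12 and 18, and nothing tells sites to aim for a window edge.
- **The WP4 clock is not certain.** Month 12 might run from the questionnaire's Day 0, since the optional extra interview is counted from there. The end-of-study alternative is not on the dose clock, and the timing figures are not shown. This lowers confidence. But under that reading, a late starter's second interview would nominally fall at month 15 rather than at the 12-month vaccination visit that the annex names.
- **Adjustment for interval belongs to the analysis plan.** That plan is not shown, so its silence is no finding. The annex sentence and the recall wording are still instructions to sites, which an analysis plan cannot change.

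A reader might also infer four stronger things that the documents do not support:

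- That the kind of centre sets every gap. It does so only for vaccinated WP4 patients; WP2 gaps follow the time of diagnosis, and the 6-month WP2 gap is an admitted exception.
- That change cannot be compared at all. Interview dates are mandatory, so gap and calendar time can be modelled.
- That the 6-month minimum is broken. The 1- and 5-month figures are window extremes, and Section 11 already forbids them; every nominal gap meets it.
- That Table 1's blank at month 6 contradicts the annex. Month 6 is a WP2 starting option, whereas Table 1 belongs to this WP4 protocol. The tables and the annex need reconciling, but that blank alone proves no error.

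**Conclusion.** The point holds as an internal inconsistency. The annex's interval and its exceptions omit a nominal 15 months for WP2 patients starting at month 3 and a nominal 9 months for vaccinated WP4 patients starting at the month-3 visit. A further 6-month case arises if the first WP4 visit is month 6, which is an assumption. The WP4 figures rest on counting month 12 from dose 1.

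The consequence is limited to two things. In vaccinated WP4 patients, unadjusted change is confounded with interval length, and interval length with centre practice, by the fractions of d shown above if drift is linear. In addition, 9- and 15-month gaps do not match the form's recall period, and recorded dates do not repair answers already given for the wrong period.

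Severity is minor to moderate. Confidence is medium, because of the unstated WP4 clock and the missing figures.

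**What to change.** 1. Correct the Annex 1 sentence so that the stated interval and its exceptions cover the WP2 month-3 start and the late WP4 starts.
2. State whether WP4 month 12 runs from dose 1 or from the questionnaire's Day 0.
3. Where the 12±3-month window allows, time the second WP4 interview as near as possible to 12 months after Day 0, and never under 6 months, as Section 11 requires. Asking for the scheduled visit closest to 12 months would not be enough, since that still selects the nominal month-12 visit.
4. Let the follow-up recall items refer to the time since the last interview.
5. Use actual interview dates, with gap and calendar time as terms, in change and difference-in-differences analyses.
6. Reconcile Annex 1 with the questionnaire rows of Tables 1 and 2.

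The cost is wording in the annex, forms and analysis text; dates are already collected. Some late starters will have no valid second interview for the change analysis. With the window closing at month 15, a first interview after month 9 (15 − 6) cannot be followed by one at least 6 months later within it.

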ANNEX 1a – Socio-economic questionnaire

To be asked on Day 0 ONLY:

Day 0 refers to the first contact with the patient, independently of whether they have been vaccinated, whether they are positive or negative, or of the time of infection, i.e. all cohort patients should be interviewed. It is crucial to record the date of the contact/interview.

1. (This is the ID that allows to identify the patient as part of ORCHESTRA and/or the original cohort): Patient ID _____ / Date of interview _____

Demographic information:

2. What is the highest level of education that you have achieved to date?
 - a. No formal school
 - b. Primary school
 - c. Secondary school
 - d. Some university
 - e. Undergraduate degree
 - f. Post-graduate degree
3. What is your current marital status?
 - a. Married
 - b. Cohabitation
 - c. Divorced/separated
 - d. Widowed
 - e. Single

Defining household as the family unit,

4. what is the total number of household members?
5. what is the number of household members below age 14?

Use of health care resources (COVID-19 UNRELATED/RELATED TO YOUR UNDERLYING CONDITIONS):

Since the beginning of the pandemic (February/March 2020), have you experienced:

6. any disruption in your routine visits (these are related to underlying conditions) and/or periodic check-ups (these may be, for example, regular gynecological visits for preventative reasons)?

| | |
|----------------|-----------|
| - Cancellation | Yes/No/NA |
| - Postponement | Yes/No/NA |
7. any interruption to the treatment you regularly follow?

- Problems accessing medication Yes/No/NA
- Postponement of your treatment session Yes/No/NA
- Cancellation of your treatment session Yes/No/NA

Socio-economic indicators

8. Which one of the following status best describes your current_labour situation?
- a. Paid Employee (in a firm/office/other)
 - b. Formal and remunerated self-employed
 - c. Informal/occasional work (with no contract)
 - d. Volunteer or other non-remunerated work
 - e. Housekeeping/look after family members
 - f. Permanent inability to work (with benefits)
 - g. Permanent inability to work (without benefits)
 - h. Temporary inability to work (with benefits): e.g., maternity leave
 - i. Unemployed without benefits
 - j. Unemployed with benefits
 - k. Retired
 - l. Student
 - m. Other

Question 9 is only for those replying a, b, c or d to question 8:

9. How many total hours a week do you work on average?
10. Thinking about your income and the income of everyone who lives in your household and contributes to the household budget, what is your current total monthly household net income (after taxes)?
- a. Less than 100€
 - b. 100€ to 299€
 - c. 300€ to 499€
 - d. 500€ to 999€
 - e. 1,000€ to 1,999€
 - f. 2,000€ to 2,999€
 - g. 3,000€ to 3,999€
 - h. 4,000€ to 4,999€
 - i. 5,000€ to 5,999€
 - j. More than 6,000€

Since the beginning of the pandemic (February/March 2020), have you:

11. had financial or liquidity problems (e.g. problems with paying rent, school fees, loan, utility bills, etc.)? Yes/No

12. received any financial or material aid (e.g. public assistance, cash-transfers, food banks, etc)?
Yes/No

Knowledge, Risk perception, Behaviour

13. How often have you recently looked for information on COVID19 (eg: efficacy and safety of vaccines, development of vaccination plans in your country, number of new cases) in the newspapers, television, radio, social networks, etc?

- a. Several times each day
- b. Once a day
- c. 2-3 times a week
- d. Once a week
- e. Less than once a week

14. On a theoretical scale from 0 to 10 (where 0 means no risk at all and 10 means maximum risk), what do you think is your current risk of infection/ re-infection?

15. On a theoretical scale from 0 to 10 (where 0 means no risk at all and 10 means maximum risk), what do you think is your current risk that, in case of infection/re-infection, there will be severe complications or even death?

16. What do you do to protect yourself against infection or re-infection, and how often? (provide an answer on frequency for all measures specified)

| | Never | Rarely | Often | Very often |
|---|--------------------------|--------------------------|--------------------------|--------------------------|
| Wash my hands with hand-soap / hydro-alcoholic solutions |  |  |  |  |
| Keep a distance of at least 2 meters from others |  |  |  |  |
| Stay at home / Avoid gathering with friends and relatives not belonging to my bubble |  |  |  |  |
| Use mask |  |  |  |  |

17. Have you been offered a vaccine by the public health system? Yes/No/NA

18. Have you accepted or will you accept to be vaccinated once you get offered a vaccine?
Yes/No/NA

19. IF NOT (for those who have not accepted or would not accept to get vaccinated): Why did/would you not accept the vaccine? (multiple replies allowed)

- a. Lack of trust in its efficacy.
- b. Fear of adverse effects.
- c. Having passed COVID-19 already, I am afraid that adverse effects will be stronger than the disease itself.
- d. Not helpful in my case as I adopt many other measures (eg: I always wear a mask).

- e. I already had COVID-19 and I am sure I will not get it again.
- f. I prefer someone else gets it before me.
- g. I believe there are other (better) ways to prevent COVID-19 than with a vaccine.
- h. Other

To be asked at the next contacts (6, 12, 18 months, whatever applies):

Follow-up interviews after Day 0.

1. (This is the ID that allows to identify the patient as part of ORCHESTRA and/or the original cohort): Patient ID _____ / Date of interview _____

Demographic information:

Defining household as the family unit,

2. what is the total number of household members?
3. what is the number of household members below age 14?

Use of health care resources (COVID-19 UNRELATED/RELATED TO YOUR UNDERLYING CONDITIONS):

Over the last 6 or 12 months, have you experienced:

4. any disruption in your routine visits (these are related to underlying conditions) and/or periodic check-ups (these may be, for example, regular gynecological visits for preventative reasons)?

- Cancellation Yes/No/NA
- Postponement Yes/No/NA

5. any interruption to the treatment you regularly follow?

- problems accessing medication Yes/No/NA
- Postponement of your treatment session Yes/No/NA
- Cancellation of your treatment session Yes/No/NA

Socio-economic indicators

6. Which one of the following status best describes your current_labour situation?
 - a. Paid Employee (in a firm/office/other)
 - b. Formal and remunerated self-employed
 - c. Informal/occasional work (with no contract)
 - d. Volunteer or other non-remunerated work
 - e. Housekeeping/look after family members
 - f. Permanent inability to work (with benefits)
 - g. Permanent inability to work (without benefits)

- h. Temporary inability to work (with benefits): e.g., maternity leave
- i. Unemployed without benefits
- j. Unemployed with benefits
- k. Retired
- l. Student
- m. Other

Questions 7 is only for those replying a, b, c or d to question 6:

- 7. How many total hours a week do you work on average?
- 8. Thinking about your income and the income of everyone who lives in your household and contributes to the household budget, what is your current total monthly household net income (after taxes)?
 - a. Less than 100€
 - b. 100€ to 299€
 - c. 300€ to 499€
 - d. 500€ to 999€
 - e. 1,000€ to 1,999€
 - f. 2,000€ to 2,999€
 - g. 3,000€ to 3,999€
 - h. 4,000€ to 4,999€
 - i. 5,000€ to 5,999€
 - j. More than 6,000€

Over the last 6 or 12 months, have you:

- 9. had financial or liquidity problems (e.g. problems with paying rent, school fees, loan, utility bills, etc.)? Yes/No
- 10. received any financial or material aid (e.g. public assistance, cash-transfers, food banks, etc)? Yes/No

Knowledge, Risk perception, Behaviour

- 11. How often have you recently looked for information on COVID19 (eg: efficacy and safety of vaccines, development of vaccination plans in your country, number of new cases) in the newspapers, television, radio, social networks, etc?
 - a. Several times each day
 - b. Once a day
 - c. 2-3 times a week
 - d. Once a week
 - e. Less than once a week

12. On a theoretical scale from 0 to 10 (where 0 means no risk at all and 10 means maximum risk), what do you think is your current risk of infection/ re-infection?

13. On a theoretical scale from 0 to 10 (where 0 means no risk at all and 10 means maximum risk), what do you think is your current risk that, in case of infection/re-infection, there will be severe complications or even death?

14. What do you do to protect yourself against infection or re-infection, and how often? (provide an answer on frequency for all measures specified)

| | Never | Rarely | Often | Very often |
|---|--------------------------|--------------------------|--------------------------|--------------------------|
| Wash my hands with hand-soap / hydro-alcoholic solutions |  |  |  |  |
| Keep a distance of at least 2 meters from others |  |  |  |  |
| Stay at home / Avoid gathering with friends and relatives not belonging to my bubble |  |  |  |  |
| Use mask |  |  |  |  |

15. Have you been offered a vaccine by the public health system? Yes/No/NA

16. Have you accepted or will you accept to be vaccinated once you get offered a vaccine? Yes/No/NA

17. IF NOT (for those who have not accepted or would not accept to get vaccinated): Why did/would you not accept the vaccine? (multiple replies allowed)

- a. Lack of trust in its efficacy
- b. Fear of adverse effects
- c. Having passed COVID-19 already, I am afraid that adverse effects will be stronger than the disease itself
- d. Not helpful in my case as I adopt many other measures (eg: I always wear a mask)
- e. I already had COVID-19 and I am sure I will not get it again
- f. I prefer someone else gets it before me
- g. I believe there are other (better) ways to prevent COVID-19 than with a vaccine.
- h. Other

